#### 9.8. 12-Lead Standard Electrocardiogram

Toxicity grading criteria for 12-lead standard ECG parameters (QTcF and PR Intervals) can be found in Table 6. Unscheduled 12-lead ECG measurements will be listed but excluded from tabular and graphical summaries, except when calculating the maximum severity post-baseline. When ECG measurements are conducted in triplicate, the mean of the triplicate values will be used for analysis.

The following ECG parameters will be presented (in order): PR interval, QRS duration, QT interval, QTcF correction (refer to protocol Section 11.4.6.1 for formula), RR interval, and ventricular rate.

12-lead standard ECG parameters will be summarized in tables and figures:

- Summary of 12-lead ECG categorical change in overall interpretation from baseline will be presented by timepoint (Table 55 for the Safety Population and Table 56 for the Safety Subset Population).
- Summary of 12-lead ECG categorical change from pre-dose baseline will be presented by timepoint (Table 57 for the Safety Population and Table 58 for the Safety Subset Population).
- The proportion of participants with mild, moderate, or severe 12-lead ECG results will be presented for QTcF Interval and PR Interval by parameter and timepoint (Table 59 for the Safety Population and Table 60 for the Safety Subset Population).
- Summary statistics of measurements and change from pre-dose baseline, including the 90% CI (see equation below), by parameter and timepoint will be summarized (Table 61 for the Safety Population and Table 62 for the Safety Subset Population).
- For ECGs collected on Day 1, summary statistics of change from time-matched baseline, including the 90% CI (see equation below), by parameter and timepoint will be summarized (Table 63 for the Safety Population and Table 64 for the Safety Subset Population).
- A categorical summary of QTcF Interval (Table 65 for the Safety Population and Table 66 for the Safety Subset Population) and PR interval, QRS duration, and RR interval (Table 67 for the Safety Population and Table 68 for the Safety Subset Population) will be presented by timepoint.
- Change from pre-dose baseline at each scheduled timepoint will be visualized using box plots for each parameter (Beginning at Figure 87 and continuing through Figure 98).

Due to the small sample size (N < 30) and unknown population variance, the 90% CI for the change from baseline will be calculated as follows:

$$\left(\bar{x} - t_{n-1,1-\alpha/2} \times \sqrt{\frac{\sigma^2}{n}}, \quad \bar{x} + t_{n-1,1-\alpha/2} \times \sqrt{\frac{\sigma^2}{n}}\right)$$

- 37 -Restricted Where,

 $\bar{x}$  is the mean change from baseline

 $t_{n-1,1-\alpha/2}$  is the t-value with n-1 degrees of freedom at a confidence level of  $\alpha$  (for 90% CI,  $\alpha = 0.1$ )

 $\sigma$  is the standard deviation

*n* is the number of observations

All individual ECG measurements will be presented in Listing 19. Overall interpretations and changes from baseline will be presented in Listing 20.

## 9.9. Otoacoustic Testing

Toxicity grading criteria for pure-tone audiometry testing can be found in Table 3. Unscheduled otoacoustic testing will be listed but excluded from tabular and graphical summaries, except when calculating the maximum severity post-baseline.

Otoacoustic test results, including ear otoscopy, pure-tone audiometry, and DPOAEs, will be summarized in tables and figures:

- For ear otoscopy, summary of change in results from baseline will be presented by ear and timepoint (Table 69 for the Safety Population and Table 70 for the Safety Subset Population).
- For pure-tone audiometry:
  - The proportion of participants with mild, moderate, or severe pure-tone audiology test results will be presented by timepoint (Table 71 for the Safety Population and Table 72 for the Safety Subset Population).
  - Summary statistics of measurements and change from baseline by timepoint, frequency, and ear will be summarized (Table 73 for the Safety Population and Table 74 for the Safety Subset Population).
  - Change from baseline at each timepoint and ear will be visualized using line plots with standard error bars for each frequency (Figure 99 and Figure 100 for frequencies 0.5, 1.0, 2.0, 4.0, 6.0 and 8.0 kHz; Figure 101 and Figure 102 for frequencies 9.0, 10.0, 11.0, 12.5, 14.5, 16.0, 18.0, and 20.0 kHz for the Safety Population and Safety Subset Population, respectively).
- For DPOAEs, including DPOAE, signal-to-noise ratio (SNR), and overall result:
  - Summary statistics of change from baseline by timepoint, frequency, and ear will be summarized (Table 75 and Table 76 for DPOAEs and Table 79 and Table 80 for SNR for the Safety Population and Safety Subset Population, respectively).
  - Summary of categorical DPAOE test results (present/absent) by timepoint, frequency, and ear will be presented (Table 77 for the Safety Population and Table 78 for the Safety Subset Population).
  - Change from baseline at each frequency and ear will be visualized using line plots with standard error bars for each scheduled timepoint and result (Figure 103 and Figure 104 for DPOAE results and Figure 105 and Figure 106 for SNR results for the Safety Population and Safety Subset Population, Respectively).

All otoacoustic testing results will be listed: ear otoscopy test results will be presented in Listing 21; pure-tone audiometry test results will be presented in Listing 22; and DPOAE test results will be presented in

Listing 23. Additionally, screening Valsalva, tympanometry, and stapedial reflex test results will be presented in Listing 24, Listing 25, and Listing 26, respectively.

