#### 3.1.2 Secondary

- To assess the safety of single IV administration of 30 mg/kg apramycin in healthy subjects.
- To assess changes in otoacoustic testing.

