- Note 3: A subject who is not sexually active and abstains from sexual intercourse can be enrolled and abstinence documented.
- 4. Males, including vasectomized men, having sexual intercourse with women of childbearing potential must agree to consistent use of condoms from IMP administration through at least 30 days after dosing, and must also agree to not donate sperm during this same time period.
  - Note: A subject who is not sexually active and abstains from sexual intercourse can be enrolled and abstinence documented.
- 5. BMI 18.0 to 32.0 kg/m^2 (inclusive) and body weight not less than 50 kg.
- 6. Subjects with normal hearing, i.e., symmetric hearing with air conduction thresholds no worse than 20 dB hearing loss for the frequencies 0.5-1-2-4-6-8 kHz bilaterally.
- 7. Normal (reproducibility 70% or better) of distortion product otoacoustic emissions (DPOAEs).

**Note**: Absence of DPOAEs at no more than two consecutive or non-consecutive DPOAEs in each ear is acceptable.

- 8. Normal otoscopic findings in the ears, normal tympanic membrane mobility and stapedial reflex present.
- 9. From the signing of the informed consent until the last follow-up visit, subjects must be willing to avoid exposure to loud music or noise.
  - Note: Noise avoidance to include continuous usage of earpieces at high volume, attending loud concerts or dance events, or using firearms or attending fireworks.
- 10. Normal lung function with Forced Expiratory Volume in the first second (FEV1) predicted  $\geq 80\%$  and FEV1/Forced Vital Capacity (FVC) > 70%.
- 11. Subjects must be willing to avoid excessive physical exercise within 48 h prior to dosing until discharge from the CTU on Day 3, and 24 h before each follow-up visit (Day  $14 \pm 3$  days and Day  $30 \pm 4$  days).
- 12. No history of acute febrile or infectious illness for at least 7 days prior to the administration of the IMP.
- 13. No history of lower respiratory tract infection within 4 weeks prior to screening.

14. Have adequate venous access for infusion and blood draws.

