#### Ototoxicity Criteria:

- Two or more subjects experience Grade 2 or higher ototoxic change of pure-tone audiometry through Day 30 ± 4 days that is confirmed by repeat testing, generally within 24 h, and assessed as related to IMP.
- A single subject experiences significant ototoxic change in DEOAEs, characterized by decrease in reproducibility to lower than 70% at three consecutive frequencies where responses were previously obtained, through Day 30 (± 4 days) and is confirmed by repeat testing, generally within 24 h:

If the predefined criteria for the halting rules are met, the SMC will review the study data and provide guidance on how to proceed.

A halted study will resume upon recommendation by the Sponsor (DMID).

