- Note 2: Highly effective contraceptive methods include: (a) surgical sterilization methods, such as tubal ligation, bilateral oophorectomy, salpingectomy, hysterectomy, or successful tubal obliteration (e.g., Essure®) with documented radiological confirmation test at least 90 days after the procedure, or (b) long-acting reversible contraception, such as progestin-releasing subdermal implants, copper intrauterine devices (IUDs), levonorgestrel-releasing IUDs.
- Note 3: A participant who is not sexually active and abstains from sexual intercourse can be enrolled and abstinence documented.
- 4. Males, including vasectomized men, having sexual intercourse with women of childbearing potential must agree to consistent use of condoms from investigational medical product (IMP) administration through at least 30 days after dosing, and must also agree to not donate sperm during this same time period.
  - Note: A participant who is not sexually active and abstains from sexual intercourse can be enrolled and abstinence documented.
- 5. BMI 18.0 to  $32.0 \text{ kg/m}^2$  (inclusive) and body weight not less than 50 kg.
- 6. Participants with normal hearing, i.e., symmetric hearing with air conduction thresholds no worse than 20 dB hearing loss for the frequencies 0.5-1-2-4-6-8 kHz bilaterally.
- 7. Normal (reproducibility 70% or better) of distortion product otoacoustic emissions (DPOAEs).
- 8. Normal otoscopic findings in the ears, normal tympanic membrane mobility and stapedial reflex present.
- 9. From the signing of the informed consent until the last follow-up visit, participants must be willing to avoid exposure to loud music or noise.
  - Note: Noise avoidance to include continuous usage of earpieces at high volume, attending loud concerts or dance events, or using firearms or attending fireworks.
- 10. Normal lung function with Forced Expiratory Volume in the first second (FEV1) predicted ≥ 80% and FEV1/Forced Vital Capacity (FVC) > 70%.
- 11. Participants must be willing to avoid excessive physical exercise within 48 h prior to dosing until discharge from the CTU on Day 3, and 24 h before each follow-up visit (Day  $14 \pm 3$  days and Day  $30 \pm 4$  days).
- 12. No history of acute febrile or infectious illness for at least 7 days prior to the administration of the IMP.
- 13. No history of lower respiratory tract infection within 4 weeks prior to screening.
- 14. Have adequate venous access for infusion and blood draws.

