- 12-lead standard ECG
  - ECG will be performed in either triplicate or single at Screening, Check-In (Day -2), Day -1 (at timepoints matching those on Day 1), Day 1 (pre-dose and 1 h, 4 h, and 16 h post-dose), Day 2 (24 h and 36 h post-dose), Day 3 (48 h and 60 h post-dose), and Day 14.
    - For ECG measurements performed in triplicate, the mean of the replicates will be used for analysis, including analyses of change from baseline.
  - At each timepoint, the overall interpretation of the ECG will be reported as Normal; Abnormal, Not Clinically Significant (NCS); or Abnormal, Clinically Significant (CS). For post-dose timepoints, the change from baseline will be also reported as No change from baseline; NCS, change from baseline; or CS, change from baseline.
  - The following parameters will be measured: PR interval, QRS interval, QT interval, corrected QT interval using Fridericia's Formula (QTcF correction), RR internal, and ventricular rate.
    - For replicate ECGs recorded on Day -1 and Day 1, the mean time-matched change-frombaseline QTcF values (ΔΔQTcF) will be evaluated to quantify the QTcF prolongation. For single ECG recoded after dosing, the mean pre-dose change-from-baseline (ΔQTcF) will also be analyzed.
- Audiology
  - The following audiology tests will be conducted:
    - Valsalva test, Tympanometry and Stapedial Reflexes at Screening only.
    - Ear otoscopy at Screening, Check-In (Day -2), Day 3, Day 14, and Day 30.

- Pure tone audiometry at standard frequencies (0.5 to 8.0 kHz) at Screening and at both standard and higher frequencies (9.0 to 20.0 kHz) at Check-In (Day -2), Day 3, Day 14, and Day 30.
- DPOAEs (1.5 to 6.0 kHz) at Screening, Check-In (Day -2), Day 3, Day 14, and Day 30.
- Physical Examination
  - A complete PE to assess general appearance; head, eyes, ears, nose, and throat (HEENT); heart, lungs, abdomen, skin, musculoskeletal system, and lymph nodes; and a neurological exam will be performed at Screening, Check-In (Day -2), Day 3 (60 h post-dose), and Day 14.
  - An abbreviated PE will be performed at Day -1. An abbreviated PE differs from a complete PE in that the abdomen and neurological system are not evaluated.
  - A symptom-directed (focused) PE may be performed on Day 1 and at any time after dosing for evaluation of TEAEs.
  - Height and weight will be measured, and BMI calculated, at Screening only. Weight only will be measured on Day -2 and Day 14.

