# Table 68:Categorical Summary of PR Interval, QRS Duration, and RR Interval by Timepoint –
Safety Subset Population

#### 14.3.8 Displays of Audiology Results

### Table 69: Ear Otoscopy Result, Post-Dose Compared to Baseline by Timepoint and Ear – Safety Population

[Implementation Note: If there are no problems at baseline (blockage of wax or foreign body or any problem other than wax or foreign body), only keep the "No Apparent Problem" rows.]

				Post-Baseline Result						
				No Apparent Problem		Blockage of Wax or Foreign Body		Any Problem Other than Wax or Foreign Body		
Ear	Time Point	Baseline Result	Ν	n	%	n	%	n	%	
Right	Day 3	No Apparent Problem	Х	х	XX	Х	XX	х	XX	
		Blockage of Wax or Foreign Body	Х	х	XX	Х	XX	х	XX	
		Any Problem Other than Wax or Foreign Body	Х	х	XX	Х	XX	х	XX	
	Day 14	No Apparent Problem	Х	х	XX	Х	xx	х	XX	
		Blockage of Wax or Foreign Body	Х	х	XX	Х	xx	х	XX	
		Any Problem Other than Wax or Foreign Body	Х	х	XX	Х	xx	х	XX	
	Day 30	No Apparent Problem	Х	х	XX	Х	xx	х	XX	
			Х	х	XX	Х	XX	х	XX	
Left	Day 3	No Apparent Problem	Х	х	XX	Х	XX	х	XX	
			Х	х	XX	Х	XX	х	XX	
	Day 14	No Apparent Problem	Х	х	XX	Х	XX	х	XX	
			Х	х	XX	Х	xx	х	XX	
	Day 30	No Apparent Problem	Х	х	XX	Х	XX	х	XX	
			Х	х	XX	Х	XX	х	XX	
Notes: $N = N$	umber of participants in the	e Safety Population with ear otoscopy results at the re-	spective timepoin	nt. Baseline = 7	The most recen	t measurement	prior to start o	f infusion.	.	

Table with similar format:

 Table 70:
 Ear Otoscopy Result, Post-Dose Compared to Baseline by Timepoint and Ear – Safety Subset Population

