### Table 75: DPOAE Measurement and Change from Baseline by Timepoint, Frequency, and Ear – Safety Population

Table with similar format:

 Table 76:
 DPOAE Measurement and Change from Baseline by Timepoint, Frequency, and Ear – Safety Subset Population
				DPOAE Result						
		Frequency		Pr	esent	Ab	sent			
Ear	Timepoint	(kHz)	Ν	n	%	n	%			
Right	Baseline	1.5	х	х	XX	х	xx			
		2.0	х	х	XX	х	xx			
		3.0	х	х	XX	х	xx			
		4.0	х	х	XX	х	xx			
		6.0	х	х	XX	х	xx			
	Day 3	1.5	х	х	XX	х	xx			
			х	х	XX	х	xx			
	Day 14	1.5	х	х	XX	х	xx			
			х	х	XX	х	xx			
	Day 30	1.5	х	х	XX	х	xx			
			х	х	XX	х	xx			
Left	Baseline	1,5	х	х	XX	х	xx			
			х	х	XX	х	xx			
Notes: N = Nu Baseline = The	mber of participants in the Safety	y Subset Population wi	th the DPAO	Es assessed at t	he respective tim	epoint and freq	uency.			

 Table 77:
 Summary of DPOAE Results by Timepoint, Frequency, and Ear – Safety Population

Table with similar format:

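### The categorical DPOAE tables (SAP Tables 77/78) show only net present/absent counts, so the number of ears that lost a response after dosing cannot be read from them.

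*SAP*

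**What the plan says.** One secondary objective in Protocol 3.1.2 is "To assess changes in otoacoustic testing". The testing schedule in SAP 4.5.1 is "DPOAEs (1.5 to 6.0 kHz) at Screening, Check-In (Day -2), Day 3, Day 14, and Day 30". The shells list five frequencies: 1.5, 2, 3, 4 and 6 kHz.

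The only categorical DPOAE summary is in SAP 9.9: "Summary of categorical DPAOE test results (present/absent) by timepoint, frequency, and ear will be presented". The Table 77 shell, "Summary of DPOAE Results by Timepoint, Frequency, and Ear – Safety Population", has columns for ear, timepoint, frequency, N, present n and %, and absent n and %. Table 78 repeats it for the Safety Subset Population. Neither has a column for baseline status.

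On entry, the note to inclusion criterion 7 in Protocol 5.1 (version 5.0, 10 July 2023) reads "Absence of DPOAEs at no more than two consecutive or non-consecutive DPOAEs in each ear is acceptable". The SAP (version 1.0, 7 February 2023) reproduces the eligibility list from protocol version 3.0, and its criterion 7 has no such note.

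For otoscopy, the same SAP section plans a shift table, "Ear Otoscopy Result, Post-Dose Compared to Baseline by Timepoint and Ear – Safety Population", which crosses each ear's baseline result with its post-dose result. Tables 55/56 do the same for ECG interpretation.

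**The concern.** A present/absent count at each visit is a prevalence. The objective is about change, and for a drug class with known cochlear risk the informative change is an ear that responded before dosing and no longer does. Movements in opposite directions cancel in a prevalence, so an unchanged absent count can mean that nothing happened or that some ears lost responses while others regained them. If every ear were present at baseline this could not occur. Once the protocol admits ears with absences, it can.

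A reader of the study report who relies on Tables 77/78 could therefore see a flat row and conclude that no ear had lost a response, which the table cannot establish.

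**Working it through.** The plan states no figure for this display, so there is none to reproduce. The check asks what the planned margins can and cannot determine.

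**Inputs.**
- N = 20 participants, 5 cohorts of 4 (SAP section 5).
- Five DPOAE frequencies per ear (Table 77 shell).
- At most two absences per ear at entry (Protocol 5.1).
- Denominators at each visit are the participants with a result at that visit (SAP 6.1).
- The documents give no rate of baseline absence. The counts *a* and *b* below are assumptions.

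**Ceiling on baseline absences.** Per ear, 2 of 5 frequencies = 40%. Over 20 participants that is 2 × 20 = 40 of 100 participant-frequency cells, or an average of 40/5 = 8 of 20 per frequency. This is an eligibility limit, not an expected value.

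**Bounds on losses.** Fix one ear and one frequency, with the same N participants at both visits. Let *a* be the number absent at baseline, *b* the number absent post-dose, L the losses (present to absent) and R the recoveries (absent to present). Then b = a + L − R, with R ≤ a and L ≤ N − a. So L lies between max(0, b − a) and min(b, N − a). The table shows only b − a.

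| a | b | Net change shown | Losses possible |
|---|---|---|---|
| 0 | 3 | +3 | 3 (exact) |
| 1 | 1 | 0 | 0 to 1 |
| 4 | 4 | 0 | 0 to 4 |
| 4 | 3 | −1 | 0 to 3 |
| 3 | 5 | +2 | 2 to 5 |

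For a = b = 4, the upper bound is 4/20 = 20% of ears, or 4/16 = 25% of those present at baseline. For a = 4 and b = 3, the table suggests improvement while up to three ears may have lost a response. With a = 0 the count of losses is exact, so with a constant N the ambiguity comes entirely from baseline absences.

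**Changing N.** Suppose 1 of 20 is absent at baseline, that participant misses Day 3, and one other participant loses the response. Day 3 then shows 1 absent of 19. Percentages are reported to whole numbers (SAP section 13): 1/20 = 5% and 1/19 = 5.3%, which also prints as 5%. One loss has occurred with no recovery, and only N, falling from 20 to 19, hints at it.

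**Pattern within a participant.** In one ear, suppose three participants are each absent at baseline at one of 2, 3 and 4 kHz. By Day 3 all three have recovered and a fourth has lost all three frequencies. The absent counts from 1.5 to 6 kHz are 0, 1, 1, 1, 0 at both visits. The table is identical although one participant has lost three adjacent responses.

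**The case against.** The strongest reply is that Tables 77/78 are not the whole DPOAE analysis. Section 9.9 also plans change from baseline for the DPOAE value (Tables 75/76) and for signal-to-noise ratio (Tables 79/80), by ear, frequency and visit. Figures 103 to 106 plot these changes. They are within-ear changes, and they supply the descriptive change statistics that Protocol 11.4.7 asks for. Listing 23 shows every participant's DPOAE value, signal-to-noise ratio and present/absent result. With 20 participants, each loss can be found by comparing rows. Tables 77/78 also include a baseline row, so net change is visible. All of this stands, and it limits the consequence. What remains is that none of these displays counts losses. The continuous tables give means, SDs, medians and extremes, and section 9.9 does not say how an absent response enters them. Listing 23 leaves change from baseline blank for the categorical result.

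A reader might infer that the halting rule is compromised. The documents do not support that. The rule in Protocol 9.5.1 concerns one subject with "decrease in reproducibility to lower than 70% at three consecutive frequencies where responses were previously obtained", confirmed by repeat testing. It is applied to individuals during the trial and takes nothing from Table 77. Nor do the documents equate an absent result in that table with reproducibility below 70%.

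A reader might also infer that the secondary endpoint will be misreported. That endpoint is the incidence of TEAEs related to auditory tests. TEAEs are recorded per participant and summarised in Tables 17 to 20, so it is not derived from Tables 77/78.

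**Conclusion.** The point holds for one display. Tables 77/78 give the net change in present/absent status but not the number of ears that lost a response, and under protocol version 5.0 the two can differ. The possible discrepancy at one ear and frequency runs from zero up to the smaller of *b* and N − *a* when the counts are level, for example 0 to 4 of 20. That size is illustrative. Version 5.0 permits baseline absences but does not show that they are expected, and masking also needs a recovery at the same ear and frequency or a changing N. If no ear is absent at baseline and N is constant, the planned table is already exact.

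It would go too far to say that DPOAE losses will be missed in the report. The data are collected and listed, and continuous change is summarised. The difference between the SAP's criterion 7 and the protocol's follows from the dates of the two documents and is an alignment matter. The change is worth making because it answers the stated objective directly and puts nothing at risk.

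**What to change.** - Re-lay Tables 77/78 in the form of Table 69: for each ear, frequency and post-dose visit, baseline present/absent crossed with post-dose present/absent. Restrict N to participants with both results.
- Report loss as present-to-absent changes divided by ears present at baseline. Report recoveries separately.
- Add a row at each visit for the number of participants with at least one present-to-absent change. In the three-frequency example this row would read 1, alongside one loss at each of 2, 3 and 4 kHz.
- While the shell is open, correct its footnote, which names the Safety Subset Population under a Safety Population title, and bring the SAP's criterion 7 into line with protocol version 5.0.

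The cost is a shell revision and some programming on data already collected. No assessment, sample size or endpoint changes. SAP section 15 allows such a change by addendum before final data lock.
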